3.2.8.4 Adequate Cardiac Function defined as:

- a. Shortening fraction of $\geq 27\%$ by echocardiogram (while not receiving medications for cardiac function), or
- b. Ejection fraction of $\geq 50\%$ by gated radionuclide study (while not receiving medications for cardiac function)
- c. Corrected QT according to the Bazett's formula QTcB must be < 450 msec (See Section 5.4.6.2 to determine QTcB)
- d. Must not have a history of myocardial infarction, severe or unstable angina, peripheral vascular disease or familial QT prolongation.
- 3.2.8.5 Adequate Blood Pressure Control defined as:

A blood pressure (BP) \leq the 95th percentile for age, height, and gender (Appendix V) measured as described in Section 5.4.1.

- Patients on stable doses of no more than one anti-hypertensive medication, with a baseline $BP \le 95^{th}$ percentile for age, height and gender (Appendix V), will be eligible.
- 3.2.8.6 Central Nervous System Function defined as:
 - a. Patients with a known history of seizures must have wellcontrolled seizures and may not be receiving enzyme-inducing anti-convulsants (See Appendix IIIA)
 - b. CNS toxicity \leq Grade 2.
- 3.2.8.7 Adequate Coagulation defined as:

PT and PTT ≤ 1.2 x upper limit of normal and an INR ≤ 1.2 .

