Serum K⁺, Ca^{++} , Mg^{++} , phosphate levels should be monitored given the risk of prolonged QTc. If serum Ca^{++} is abnormal, ionized calcium should be obtained and interventions based on ionized calcium only.

Pazopanib should be held and an EKG obtained for

- Hypokalemia or hyperkalemia \geq Grade 2
- Hypocalcemia or hypercalcemia \geq Grade 3
- Hypophosphatemia or hyperphosphatemia \geq Grade 3
- Hypomagnesemia or hypermagnesemia \geq Grade 3

These laboratory values should be corrected as soon as possible in a manner consistent with good medical judgment. Pazopanib may be resumed at a reduced dose when:

- Hypokalemia or hyperkalemia is Grade 1 or within institutional limits
- Hypocalcemia or hypercalcemia is \leq Grade 2
- Hypophosphatemia or hyperphosphatemia is \leq Grade 2
- Hypomagnesemia or hypermagnesemia is \leq Grade 2.

Even though pazopanib administration is allowed at these lower laboratory toxicity grades, every effort should be made to correct the abnormal lab values to normal if possible.

5.4.5 Proteinuria:

- If urinalysis shows ≥ trace protein then obtain a urine protein: creatinine ratio (UPC).
- If the UPC is \geq 1, then obtain a 24-hour urine collection for protein estimation.
- If the urine protein is ≥ 3.5 g/24-hours then hold pazopanib and reassess urine protein weekly.
- If the urine protein decreases to < 3.5 g/24 hours in < 21 days then resume pazopanib at a reduced dose.
- Monitor the 24 hour urine protein or UPC weekly for 2 consecutive weeks once pazopanib is resumed.
- If pazopanib is held for ≥ 28 days then the patient must be removed from protocol therapy.
- 5.4.6 Cardiac Function:

5.4.6.1 Left Ventricular Systolic Dysfunction:

Adverse events & descriptions	Dose Modifications & Evaluations
LV EF <lln <math="" but="">\geq 50% OR</lln>	Continue drug and repeat Echo on Day 28 of
LV SF \leq LLN but \geq 24% without symptoms	subsequent cycle
of cardiac dysfunction	
LV EF 40 – 49% OR	Hold pazopanib and obtain repeat Echo in 7
LV SF 15 – 23% OR	days. If toxicity confirmed, then remove
Absolute decrease in SF \geq 8 percentage	from protocol therapy.
points from baseline	If not confirmed, then resume drug at reduced
	dose and repeat Echo 14 and 28 days after
	resuming pazopanib. If any 2 Echos
	demonstrate LV EF 40 - 49% OR LV SF 15 -
	23%
	$OR \ge 8$ percentage point decrease in SF then
	remove from protocol therapy and refer to
	pediatric cardiologist
Grade 3 LV EF decreased OR	Remove from protocol therapy – refer to

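### Rows 1 and 2 of the left-ventricular dysfunction table overlap: one asymptomatic echocardiogram can call both for continuing and for holding pazopanib

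*Protocol*

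**What the plan says.** The table in Protocol Section 5.4.6.1 has three rows. The first two matter here.

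- **Row 1.** Left-ventricular EF below LLN but at least 50%, or SF down to the LLN range but still at least "24% without symptoms" of cardiac dysfunction. The instruction is "Continue drug and repeat Echo on Day 28 of" the subsequent cycle.
- **Row 2.** EF 40–49%, or SF 15–23%, or "Absolute decrease in SF" of 8 or more percentage points from baseline. The instruction is "Hold pazopanib and obtain repeat Echo in 7" days. Then, "If toxicity confirmed, then remove" the patient from protocol therapy; "If not confirmed, then resume drug at reduced" dose, with further echocardiograms 14 and 28 days later.

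Entry under Section 3.2.8.4 requires an SF of at least 27% "by echocardiogram (while not receiving medications for cardiac function), or" an EF of at least 50% by radionuclide study. Neither has an upper bound.

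Three other places touch the table: the note beneath it, which covers only the imaging method; footnote 16 to the Section 7.1 evaluation table; and Section 7.2.3. None says which row governs if both are met.

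**The concern.** The 8-point limb of row 2 stands alone. It is joined by OR and carries no condition on the absolute SF or on symptoms. Row 1, in turn, sets no limit on the size of the fall. A patient who starts with a comfortably normal SF can therefore fall by 8 or more points and still land in the row 1 band.

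The consequences differ and are hard to undo. Under row 1 the patient stays on the same dose until an echocardiogram at the end of the following 28-day cycle. Under row 2 drug stops at once, with a repeat in 7 days. If the finding is confirmed the patient comes off, and Section 8.2 does not allow retreatment after permanent discontinuation. If it is not confirmed the dose is reduced, and Section 4.1.2 does not allow it to go back up. Two sites could follow the table literally and manage the same echocardiogram differently.

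**Working it through.** There is no plan figure to reproduce; the check is whether two rules can both apply.

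**Inputs.** Row 1 lower bound 24% and row 2 fall of 8 points (Section 5.4.6.1); entry SF of at least 27% (Section 3.2.8.4). LLN for SF is not stated, so it is an assumption, varied from 25% to 30%.

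**Condition for overlap through SF, no symptoms.** 24 ≤ SF < LLN, and baseline − SF ≥ 8.

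**Lowest baseline that can overlap.** At SF 24% the baseline must be at least 24 + 8 = 32%, which is eligible. For baselines of 27–31%, a fall of 8 or more gives an SF of at most 31 − 8 = 23%, below the row 1 band, so the two SF criteria cannot both be met.

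**Example.** 35 − 25 = 10 points, so row 2 is met. SF 25% is at least 24% and, if LLN is above 25%, below LLN, so row 1 is met.

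**Baseline from which every whole-number SF in the row 1 band also meets row 2.** This is (highest SF in the band) + 8.

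| Assumed LLN (%) | Row 1 band (%) | Lowest baseline with any overlap (%) | Baseline from which the whole band overlaps (%) |
|---|---|---|---|
| 25 | 24 | 32 | 24 + 8 = 32 |
| 26 | 24–25 | 32 | 25 + 8 = 33 |
| 27 | 24–26 | 32 | 26 + 8 = 34 |
| 28 | 24–27 | 32 | 27 + 8 = 35 |
| 29 | 24–28 | 32 | 28 + 8 = 36 |
| 30 | 24–29 | 32 | 29 + 8 = 37 |

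The SF criterion may be printed as at or below LLN rather than below it; the extracted text is not a safe guide. On that reading the last column rises by one point and the 32% is unchanged.

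**Between those limits a patient can still be in row 1 alone.** With LLN 27%, 33% to 26% and 32% to 25% are both 7-point falls. With LLN 28%, so is 34% to 27%.

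**A second route.** Row 1's EF limb can also coincide with an SF fall of 8 or more points when both measures are reported. The 32% floor does not apply to that route.

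**The case against.** The strongest answer is that the protocol already has a tie-break. Section 5 opens with a general rule, repeated in Section 5.2, that dose modifications follow the worst preceding toxicity. The table also rises in severity from continuing, to holding, to removal, and row 2 uses the 8-point fall again as a removal criterion after rechallenge. On this view a patient who meets the more severe row is managed under it.

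Much of that stands: it makes the stricter reading the more natural one. But the rule is generic and does not rank these rows, and row 1 is itself an express instruction to continue. The protocol can write exclusions into a row when it wants them. The ALT rows in Section 5.4.3, for example, are limited to patients without bilirubin elevation. The Amendment 3 log, taken only as evidence of intent, shows the row 2 bands trimmed from EF 40–50% and SF 15–24% to 40–49% and 15–23%, which removed the shared boundary with row 1. The 8-point limb still crosses it.

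A reader might infer more than the documents support:

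- **That most asymptomatic declines into the row 1 band fall in the overlap, or that only baselines of 27–31% escape it.** The second is wrong by the 7-point examples. The first has no basis: the documents give neither LLN nor any distribution of baseline SF or of SF falls.
- **That the Phase I experience gives the frequency.** Section 2.4.1 reports asymptomatic decreases in left-ventricular systolic function in 3 of 27 patients at the MTD. All were reversible, and drug was successfully reintroduced in two. That is the rate of any such decrease; no SF values are given.
- **That the trial's cardiac-scan results are compromised.** SAP Sections 9.4.4 and 11.8 categorise change in LVEF; no SF summary is specified.

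**Conclusion.** The point holds as a wording inconsistency within one table. For an asymptomatic patient with baseline SF of at least 32%, an on-study SF between 24% and LLN, and a fall of 8 or more points, rows 1 and 2 give incompatible instructions. The general worst-toxicity rule is only a partial tie-break.

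The overlap exists at every LLN tried from 25% to 30%. In whole numbers, it covers the entire row 1 SF band only from a baseline of 34% if LLN is 27%, or 35% if LLN is 28%, taking row 1 as strictly below LLN. Its frequency cannot be determined from the documents.

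The effect is on patient management and on discontinuations for adverse events, which SAP Section 11.5 summarises. The SAP's LVEF summaries are not affected. SAP Section 4.3 records that the study was declared futile after stage 1 and that termination was approved, so the prospective benefit of a correction is limited to patients still being dosed.

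**What to change.** Reconcile rows 1 and 2 of Section 5.4.6.1 so that they are mutually exclusive, by saying in the table how an SF of at least 24% with a fall of 8 or more points from baseline is handled. Alternatively, state in the table which row takes precedence when both are met. If the worst-toxicity rule is meant to decide it, say so there. The sponsor and COG decide which instruction applies; this review takes no view on that. The study report should state which row was applied wherever a patient met both.

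The cost is one line in the table and a letter to sites.

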3.2.8 Organ Function Requirements

- 3.2.8.1 Adequate Bone Marrow Function defined as:
 - Peripheral absolute neutrophil count (ANC) $\geq 1000/\mu L$
 - Platelet count ≥75,000/µL (transfusion independent, defined as not receiving platelet transfusions within a 7day period prior to enrollment); and
 - Hemoglobin ≥ 8.0 g/dL (may receive RBC transfusions)

Note: Patients with bone marrow involvement will be eligible for study (provided they meet the criteria above) but will not be evaluable for hematologic toxicity.

- 3.2.8.2 Adequate Renal and Metabolic Function defined as:
 - a. Creatinine clearance or radioisotope glomerular filtration rate $(GFR) \ge 70 \text{ mL/min}/1.73 \text{ m}^2, \text{ or}$
 - b. A serum creatinine based on age/gender as follows:

Age	Max Crea	Maximum Serum Creatinine (mg/dL)	
	Male	Female	
1 to $<$ 2 years	0.6	0.6	
2 to < 6 years	0.8	0.8	
6 to < 10 years	1	1	
10 to < 13 years	1.2	1.2	
13 to $<$ 16 years	1.5	1.4	
\geq 16 years	1.7	1.4	
The threshold creatinine values in this table were derived from the			

The threshold creatinine values in this table were derived from the Schwartz formula⁴³ for estimating GFR utilizing child length and stature data published by the CDC.

- c. Urine protein:creatinine (UPC) ratio of <1; or a urinalysis that is negative for protein; or 24-hour urine protein level < 1000 mg/dL (see Appendix IV).
- d. Adequate thyroid function: either normal TSH or on a stable dose of thyroid replacement for at least 4 weeks (see Section 3.3.2.8)
- e. No more than Grade 1 abnormalities of:
 - a. Potassium
 - b. Calcium (confirmed by ionized calcium)
 - c. Magnesium
 - d. d. Phosphorous

Oral supplementation is allowed.

3.2.8.3 Adequate Liver Function defined as:

- a. Total bilirubin ≤ 1.5 x upper limit of normal (ULN) for age;
- b. SGPT (ALT) $\leq 2.5 \text{ x ULN}$ (for the purpose of this study, the ULN for SGPT is 45 U/L);
- c. Serum albumin $\ge 2 \text{ g/dL}$.
- d. Must not have active liver or biliary disease (with the exception of Gilbert's syndrome or asymptomatic gallstones, liver metastases or otherwise stable chronic liver disease per investigator assessment).
 - NOTE: Stable chronic liver disease should generally be defined by the absence of ascites, encephalopathy, coagulopathy, hypoalbuminemia, oesophageal or gastric varices, persistent jaundice, or cirrhosis.
- e. No known positivity of hepatitis B surface antigen (HBsAg) or of positive hepatitis C antibody

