Grade 3 LV SF decreased	pediatric cardiologist

• Cardiac evaluation by Echo but MUGA (Multiple-Gated Acquisition) may be used if clinically indicated

5.4.6.2 QT Prolongation:

Guidelines for the management of prolonged QT interval are as follows: Measure the QT interval (from the start of the Q wave to the end of the T wave) and the preceding RR interval. The corrected QT interval using the Bazett's formula (QTcB interval) will be calculated as the QT interval (msec) divided by the square root of the RR interval (msec). Only the Bazett's formula should be used to calculate the corrected QT interval.

- QTcB interval < 500 msec: No specific therapy needed. Continue pazopanib at the same dose. Serum K⁺, Ca⁺⁺, Mg⁺⁺, and Phos should be monitored and repleted if low (see Section 5.4.4).
- QTcB interval ≥ 500 msec: Hold pazopanib, review concomitant medications, and replete serum K⁺, Ca⁺⁺, Mg⁺⁺, and Phos as needed. The EKG should be repeated within 7 days and if the QTcB interval is < 500 msec then resume pazopanib at a reduced dose. If the QTcB interval remains ≥ 500 msec, the patient must be removed from protocol therapy.
- 5.4.7 Delays in Wound Healing:

Patients treated with VEGF blocking agents appear to have an increased risk of wound healing complications. Therefore, if patients require elective major surgery on study, pazopanib should be held for 14 days prior to surgery and for 14 days after surgery (see Section 3.3.7). Pazopanib should not be restarted if there is evidence of wound healing complications such as a wound infection. Patients who require surgery less than 14 days from treatment with pazopanib should be monitored closely for wound complications. Patients who require major surgery during Cycle 1 of therapy must be removed from protocol therapy.

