The corrected QTcB interval (QTcB) will be listed for each patient and summarized at each scheduled assessment time. Change from baseline will be summarized and an analysis of central tendency (means, medians) will be presented. A categorical analysis for each QTcB parameter will be performed to determine the number of patients at each time point for the following categories:

- QTcB. <450, 450 to <480, 480 to 500, and >500 msec.
- QTcB change from baseline, 30 to <60 msec, and ≥ 60 msec.

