13.6 APPENDIX IV: URINE PROTEIN TO CREATININE (UPC) RATIO

Clinical Meaning of UPC

There is a good correlation between the ratio of urine protein to urine creatinine concentrations (UPC) in a random urine sample and the amount of protein excreted in a 24-hour urine collection period. ⁴⁸ Thus, the UPC ratio from a single random urine sample permits estimation of the 24-hour urine protein excretion. The creatinine excretion is fairly constant throughout the day regardless of changes in urine flow rate:

- Men excrete 20 mg to 25 mg of creatinine/kg of body weight/day
- Women excrete 15 mg to 20 mg of creatinine/kg of body weight/day
- Normal protein excretion is <100 mg to 150 mg per 24 hours.
- The UPC ratio is roughly equal to the 24-hour urine protein excretion in g/day

Calculating UPC Ratio

UPC ratio = (Urine protein [mg/dL]) / (urine creatinine [mg/dL]) = numerically equivalent to grams (g) protein excreted in urine over 24 hours.

Example: If a patient has a urine protein concentration of 90 mg/dL and urine creatinine concentration of 30 mg/dL,

then UPC ratio = $\frac{90(mg/dL)}{30 (mg/dL)} = 3$

UPC ratio of 3 correlates to roughly 3g of protein excretion in a 24-hour period.

Units for UPC ratio

UPC is a calculated ratio. The guidelines in the protocol are based on having urine protein and urine creatinine measured in the same units (e.g., mg/dL). The International System of Units (SI) units for urine protein and urine creatinine are not the same, so these must be converted to mg/dL before calculating the ratio. For reference, the conversion factors for commonly used units for protein and creatinine are provided below.

Starting units	Conversion to mg/dL
Protein (g/L)	Multiply by 100
Creatinine (µmol/L)	Divide by 88.4
Creatinine (mmol/L)	Multiply by 11.3

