#### **ECG Corrected QT Intervals**

The QTc values based on Bazett's formula is derived by QT interval / ((RR interval/1000)^1/2), where RR interval is in msec.

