#### 9.4.2. ECG Parameters

The following criteria will be used to flag electrocardiogram (ECG) values that are values of potential clinical importance:

To identify QTc (Bazett's) values of potential clinical importance, NCI-CTCAE v4.0 will be used to assign grades (see adverse event 'Electrocardiogram QT corrected interval prolonged'). Note that there is a slight inconsistency between CTCAE v4.0 and ICH E14 (Absolute QTc interval prolongation). It was decided to align with CTCAE for the oncology standard categories.

ECG Parameter	Potential Clinical Importance (PCI) Range	Unit
Absolute QTcB interval	<450	Msec
	≥450 to <480 (Grade 1)	
	≥480 to <500 (Grade 2)	
	≥500 (Grade 3)	
Absolute QTcF interval	<450	Msec
	≥450 to <480 (Grade 1)	
	≥480 to <500 (Grade 2)	
	≥500 (Grade 3)	
Increase from baseline	Increase of $\geq 30$ to $< 60$	Msec
QTcB	Increase of $\geq 60$	

The following criteria will be used to flag other ECG values that are values of potential clinical importance:

ECG Parameter	Potential Clinical Importance (PCI) Range	Unit
PR interval	<110 (L) and >220 (H)	Msec
QRS interval	<75 (L) and >110 (H)	Msec

Normal values per age group for QTcB and QTcF, derived from the 2nd and 98th percentile values in healthy children will be used to identify the values out of normal ranges within each age group.

Age group	0-1 month	1-3 month	3-6 month	6-12 month	1-3 years	3-5 years	5-8 years	8-12 years	12-16 years
QTcB (ms) Boys	413 (378, 448)	419 (396, 458)	422 (391, 453)	411(37 9, 449)	412 (383, 455)	412 (377, 448)	411(37 1, 443)	411(37 3, 440)	407 (362, 449)
QTcB (ms) Girls	420(37 9, 462)	424(38 1, 454)	418 (386, 448)	414(38 1, 446)	417(38 1, 447)	415(38 8, 442)	409 (375, 449)	410 (365, 447)	414(37 0, 457)

Data shown above as median  $(2^{nd} \text{ percentile}, 98^{th} \text{ percentile})$ 

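### Two operative protocol rules carry the wrong unit: QTcB is computed with RR in msec (31.6 times too small), and the 24-hour urine protein limit is given in mg/dL

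*Protocol*

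**What the plan says.** **QTcB.** Protocol 5.4.6.2 asks sites to measure QT and the preceding RR interval and to compute QTcB as QT (msec) "divided by the square root of the RR interval (msec". It allows no correction other than Bazett's. The same section holds pazopanib at 500 msec or more, and removes the patient if the repeat ECG within 7 days is still at or above 500. Eligibility criterion 3.2.8.4c relies on the same calculation: "QTcB must be < 450 msec (See Section 5.4.6.2 to determine QTcB". The safety categories in Protocol 9.8.2.6 are on the usual scale: "450 to <480, 480 to 500, and >500 msec". SAP 9.2.11 gives the formula as "QT interval / ((RR interval/1000)^1/2), where RR interval is in msec".

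**Urine protein.** Criterion 3.2.8.2c is met by any one of three limbs: UPC below 1, a urinalysis negative for protein, or a "24-hour urine protein level < 1000 mg/dL". It refers to Appendix IV, which works in mass per day: "Normal protein excretion is <100 mg to 150 mg per 24 hours" and "The UPC ratio is roughly equal to the 24-hour urine protein excretion in g/day". The dose-hold rule in 5.4.5 is also in mass per day, at 3.5 g per 24 hours.

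Section 3.2 says that the inclusion criteria are to be taken at face value, with no waivers.

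**The concern.** The two controlling documents define the same variable, QTcB, in ways that cannot both be right, and the protocol's version is the one that sites are told to apply. It feeds an eligibility limit and a hold and removal rule for a drug whose background section (2.3.1) reports QT prolongation and torsade de pointes. A formula that always returns a number far below the limit switches off both rules.

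The urine criterion names a 24-hour quantity but limits a concentration. Its three limbs are alternatives, so the loosest one governs. If the limit is looser than intended, patients with substantial proteinuria can enter on a drug for which proteinuria is a listed toxicity with its own hold rule.

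**Working it through.** **1. QTcB: ratio of the two formulas**

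- Protocol 5.4.6.2: QT / sqrt(RR), RR in msec.
- SAP 9.2.11: QT / sqrt(RR/1000), RR in msec, reading the printed exponent as one half.
- Ratio SAP/protocol = sqrt(1000) = 31.62, whatever QT and RR are.

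Check at 60 bpm (RR = 1000 msec): the SAP formula divides by 1 and leaves QT unchanged, whereas the protocol formula divides by 31.6.

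Check on a typical patient, using the SAP 9.4.2 and 9.4.3 medians for boys aged 12-16 (QTcB 407 msec, heart rate 73 bpm): RR = 60000/73 = 822 msec and QT = 407 × sqrt(0.822) = 369 msec. The SAP formula returns 407. The protocol formula returns 369/sqrt(822) = 12.9.

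**2. Effect on the limits**

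| Correct QTcB (msec) | Value by the protocol formula |
|---|---|
| 450 (eligibility) | 450/31.62 = 14.2 |
| 500 (hold) | 500/31.62 = 15.8 |
| 440 to 457 (SAP 9.4.2 98th percentiles, ages 1-16) | 13.9 to 14.5 |

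The last row comes from the SAP table headed "Normal values per age group for QTcB and QTcF".

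The QT needed to reach a limit by the printed formula is the limit × sqrt(RR). SAP 9.4.3 gives heart-rate limits of 50 to 180 bpm over ages 1-16, so RR runs from 1200 down to 333 msec.

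- For 450: 450 × sqrt(1200) = 15,588 msec, and 450 × sqrt(333.3) = 8,216 msec.
- For 500: 500 × sqrt(1200) = 17,321 msec, and 500 × sqrt(333.3) = 9,129 msec.

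These are QT intervals of 8 to 17 seconds, or 13 to 27 times the RR interval. That is impossible, so on a literal reading neither limit can be reached.

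**3. Urine protein**

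The intended value follows from Appendix IV, whose worked example reproduces: 90/30 = 3, read as about 3 g per 24 hours. UPC below 1 therefore corresponds to about 1 g (1000 mg) per 24 hours, which is the printed number with a different unit.

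The printed limit, converted: 1000 mg/dL × 10 dL/L × V L/day = 10 × V g per 24 hours.

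| V (L/day) | Protein at the printed limit (g/24 h) |
|---|---|
| 0.1 | 1 |
| 0.35 | 3.5 (the 5.4.5 hold level) |
| 0.5 | 5 |
| 1.0 | 10 |
| 1.5 | 15 |

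The documents give no urine volumes, so 0.5 to 1.5 L/day is an assumed range. The break-even at 0.1 L/day and the crossing at 0.35 L/day need no such assumption.

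**The case against.** The strongest reply is that no competent reader would apply either rule as printed. Bazett is named, the limits are in msec, the categories and paediatric percentiles run in the hundreds, and a result near 13 would be noticed at once. That is persuasive on likely harm. It does not make the formula right: 5.4.6.2 tells sites to measure and calculate, and nothing says that machine-computed values are used.

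Other safeguards also exist. Familial QT prolongation and drugs with a known torsades risk are excluded. An attributable Grade 3 non-hematologic toxicity is a DLT that leads to a hold under 5.3.1, and SAP 9.4.2 places QTc of 500 msec or more at Grade 3. That route still needs a correctly computed QTc.

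For urine, 5.4.5 is in the right unit, and urinalysis is scheduled on Cycle 1 Day 1 (4.9) and before each later cycle (7.1). A patient at or above 3.5 g per 24 hours should be held soon after entry, so the lasting gap is roughly 1 to 3.5 g per 24 hours, not the 5 to 15 g in the table.

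The instruction to read criteria literally belongs to the eligibility sections. It does not extend to 5.4.6.2, which describes its rules as guidelines.

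A reader might go further and infer that the QTcB analysis is wrong, or that Per Protocol membership must be re-screened. The documents support neither inference. The SAP uses the correct formula, and SAP 11.8 tabulates baseline QTc in bands split at 450 msec, so a last pre-dose value of 450 or more would already be visible. A patient who met the printed urine limit met the criterion as written, and the deviations that lead to Per Protocol exclusion sit in a separate specification that is not among these documents.

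**Conclusion.** Both rules are wrong as written, in current protocol text. The QTcB error is exactly sqrt(1000) = 31.6 at every heart rate, contradicts SAP 9.2.11, and on a literal reading disables one eligibility limit and one hold and removal rule. The urine error affects eligibility only. It loosens the intended limit of about 1 g per 24 hours at any output above 0.1 L/day, with 5.4.5 as a backstop at 3.5 g per 24 hours. How much it loosens the limit beyond that depends on urine volumes, which are assumed here.

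Practical impact is limited. The documents do not show that any patient was wrongly enrolled or that a hold was missed, and ORR and the two-stage decision rule are untouched. SAP 4.3 records that the study was declared futile after stage 1, so this is mainly a correction of the record. It remains worth making because both errors sit in safety rules and cost almost nothing to put right.

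**What to change.** - **Protocol 5.4.6.2:** define QTcB as QT (msec) divided by the square root of RR in seconds, that is RR in msec divided by 1000, to agree with SAP 9.2.11.
- **Protocol 3.2.8.2c:** give the 24-hour limit as below 1000 mg per 24 hours, to agree with UPC below 1 and Appendix IV.

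The cost is two unit corrections in the protocol. No clinical threshold, SAP derivation, data collection or analysis changes.
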